#### **11.4.14. Regulatory Reporting**

Vyriad (or designee) will process and evaluate all SAEs as soon as the reports are received. For each SAE received, Vyriad will make a determination as to whether the criteria for expedited reporting have been met.

Vyriad (or designee) will submit SAEs that meet the criteria for expedited reporting to the Regulatory Authorities in accordance with local regulations governing safety reporting.

Reporting of SAEs by the investigator to his or her IRB will be done in accordance with the standard operating procedures and policies of the IRB. Adequate documentation must be maintained showing that the IRB was properly notified.

#### **11.4.15. Follow-up Information on a Serious Adverse Event**

Appropriate diagnostic tests should be performed and therapeutic measures, if indicated, should be instituted. Appropriate consultation and follow-up evaluations should be carried out until the event has returned to baseline or is otherwise explained by the investigator.

Follow-up data concerning the SAE (e.g., diagnostic test reports, physician's summaries, etc.) also must be submitted to Vyriad, as they become available, by telefax or email transmission, until resolution of the SAE.

### **11.5. Other Safety Considerations**

#### **11.5.1. Medication Errors**

Any medication error that results in an AE, even if it does not meet the definition of serious, requires reporting within 24 hours to the Medical Monitor.

#### **11.5.2. Follow-Up of Serious Adverse Events**

Any SAE that led to treatment discontinuation (including clinically significant abnormal laboratory values that meet these criteria) and is ongoing 30 days after last dose of study treatment must be followed until either resolution of the event or determination by the investigator that the event has returned to baseline/resolved, Grade 1 or has become stable. This follow-up guidance also applies to SAEs that occur *more than 30 days after last dose* of study treatment.

### **11.6. Safety Monitoring**

Patients will be closely monitored for adverse events of interest through standard safety reporting as well as regular medical review of safety data outputs from both the clinical and pharmacovigilance databases. SAEs, including deaths, and withdrawals due to adverse events will also be closely monitored.

## **12. STUDY ASSESSMENTS AND PROCEDURES**

Once Vyriad has confirmed a cohort slot availability, an informed consent must be obtained before any study-specific samples are taken or study-specific tests or evaluations are conducted. Screening assessments should be performed within 21 days before the IT dose of study drug is administered on Day 1. Study eligibility will be based on satisfying all of the study inclusion and exclusion criteria for each cohort.

Study Day 1 is defined as the date the study drug is administered via IT injection, with subsequent study days numbered sequentially thereafter.

If significant changes from baseline are noted during the course of the study, additional unscheduled clinic visits may be undertaken by the investigator, or requested by the sponsor, in order to determine both the relevance of the finding(s) and the duration of the event(s).

### **12.1. Procedures to be Performed**

#### **12.1.1. Informed Consent**

The Investigator must obtain documented consent and HIPAA waiver from each potential patient prior to participating in a clinical trial. Adequate time must be allowed for the patient to ask questions and make a voluntary decision. Consent must be documented by the patient's dated signature on a consent form along with the dated signature of the person conducting the consent discussion.

A copy of the signed and dated consent form should be given to the patient before participation in the trial.

The initial informed consent form, any subsequent revised written informed consent form and any written information provided to the patient must receive the IRB/ERC's approval/favorable opinion in advance of use. The patient should be informed in a timely manner if new information becomes available that may be relevant to the patient's willingness to continue participation in the trial. The informed consent will adhere to IRB/ERC requirements, applicable laws and regulations and Sanford Research requirements.

No protocol-specific procedures, including screening procedures that are not standard of care procedures, are to be performed until the patient has signed and dated an IRB/IEC-approved ICF.

#### **12.1.2. Inclusion/Exclusion Criteria**

All inclusion and exclusion criteria will be reviewed by the investigator or qualified designee to ensure that the patient qualifies for the trial. An enrollment form will be completed by the investigator and sent to Vyriad for review prior to enrollment being permitted.

#### **12.1.3. Demographics and Height**

Demographic data will include age, sex, and self-reported race/ethnicity. Height will be recorded at screening.

#### **12.1.4. Medical History**

A medical history will be obtained by the investigator or qualified designee. Medical history will include all active conditions, and any condition diagnosed within the prior 10 years that are considered to be clinically significant by the Investigator. Details regarding the disease for which the patient has enrolled in this study will be recorded separately and not listed as medical history.

#### **12.1.5. Complete and Abbreviated Physical Examinations**

The investigator or qualified designee will perform a complete physical exam during the screening period. Clinically significant abnormal findings should be recorded as medical history.

For cycles that do not require a full physical exam per the Schedule of Assessments, the investigator or qualified designee will perform a directed physical exam as clinically indicated prior to trial treatment administration.

Weight will be taken with each physical exam (complete or abbreviated).

#### **12.1.6. Vital Sign Measurements**

The investigator or qualified designee will take vital signs at screening, prior to the administration of the dose of trial treatment and at other specified time points per the Schedule of Assessments, after the patient has been sitting for 5 minutes. Vital signs should include temperature (Celsius/Fahrenheit), pulse (beats per minute), respiratory rate (breaths per minute), weight and blood pressure (mm Hg).

Please note that blood pressure measurements are to be performed using appropriate technique (per guidelines of the American Heart Association). Specifically, patients should be seated quietly for at least 5 minutes in a chair with their backs supported, their feet flat on floor (legs uncrossed), and their arms bared on a hard surface, with the arm slightly abducted and bent, with palm up and the midpoint of upper arm at heart level. Correct cuff and bladder size should be utilized. Record cuff size, arm used, and patient's position (if not seated).

#### **12.1.7. Eastern Cooperative Oncology Group Performance Status (ECOG PS)**

The investigator or qualified designee will assess the patient's ECOG performance status (see [Appendix 1](#)) as specified in the Schedule of Assessments.

#### **12.1.8. Hematology, Serum Chemistries, Coagulation and Urinalysis**

Samples for laboratory assessments (hematology, serum chemistries, coagulation and urinalysis) are to be collected (see [Table 2](#)). Laboratory tests for screening should be performed within 14 days prior to treatment initiation. Blood samples for hematology, serum chemistry, coagulation and urinalysis will be prepared using standard procedures. Urinalysis will only be conducted as clinically indicated (see [Table 2](#)).

Abnormalities in clinical laboratory tests that lead to a change in patient management are considered clinically significant for the purposes of this study, and will be recorded on the AE CRF page. If laboratory values constitute part of an event that meets criteria defining it as serious, the event (and associated lab values) must be reported as an SAE (see [Section 11.3](#)). Furthermore, at screening, a blood sample will be analyzed for HIV and hepatitis B and C serology.

**12.1.9. Pregnancy Test**

Serum pregnancy tests are to be performed for females of childbearing potential within 7 days of study treatment.

**12.1.10. Virology Screening**

HIV, HPV and HCV virology will be performed at screening to ensure eligibility.

**12.1.11. Assessment of Peripheral Immune Response to Viral Administration**

Measles virus specific immunity will be measured by means of measuring anti-measles virus specific antibodies (IgG).

Assessments will be performed at screening and at the day 36 assessment.

**12.1.12. Disease and Response Assessments****12.1.12.1. Baseline Tumor Imaging**

Initial tumor imaging (diagnostic CT scan) must be performed within the 21-day screening period prior to enrollment to confirm measurable disease. Patient must have 2 identified target lesions, one for injecting and one as a control. Baseline imaging must be performed per RECIST 1.1. The baseline imaging scan should be reviewed by each individual site prior to enrollment to confirm measurable disease.

**12.1.12.2. Tumor Imaging During Trial**

Tumor imaging will occur on day 36 after MV-NIS injection. After Cycle 1, tumor measurements per RECIST 1.1 will be conducted every 3 cycles (i.e. cycles 4, 7, 10 etc.) until PD. For patients whose disease progresses, immune-related response criteria may be used by the investigator to continue therapy in the presence of potential pseudoprogression or tumor flare with clinical stability as appropriate until PD is confirmed.

**12.1.13. Viral Bio-distribution Imaging (SPECT/CT)**

Single-photon emission computerized tomography (SPECT/CT) is the scan that will be utilized to assess viral bio-distribution and elimination. SPECT/CT imaging will be performed after IV  $^{99m}\text{Tc}$  administration (2 hours after 20 mCi) at baseline and day 8. If there is uptake in organs other than the thyroid, stomach, or salivary glands on day 8, an additional SPECT/CT imaging study will be performed on day 15 to document elimination of the virus and infected cells. If the SPECT/CT is positive on day 15 then follow up imaging will be performed on day 36 if the day 15 scan is positive.

**12.1.14. MV-NIS Administration**

Trial treatment with MV-NIS will be given by appropriately trained surgical and interventional radiology sub-investigators. MV-NIS will be administered IT in one single tumor location as agreed upon by the principal investigator and administering sub-investigator using a 21- or 22-gauge needle or Quadrafuse® needle (or per radiologist's discretion) on day 1. Refer to [Section 9.1.5](#).

### **12.1.15. Atezolizumab IV Infusion**

Atezolizumab will be administered starting on day 15 and then every 3 weeks thereafter.

### **12.1.16. Prior and Concomitant Medications**

All concomitant medications will be recorded 4 weeks prior to signs the informed consent form through the 30 day follow-up period.

### **12.1.17. Adverse Event Assessments**

Information regarding the occurrence of AEs and SAEs will be collected from the time the patient signs the informed consent form throughout their participation in the study, including the 30 days after the patient's last dose of study drug, unless a new treatment has been started. Any known untoward event that occurs beyond the AE reporting period that the investigator assesses as possibly related to study drug also should be reported to Vyriad.

**Note:** AEs resulting in a patient's permanent discontinuation from the study, regardless of seriousness or relationship to study drug, MUST be promptly reported to the sponsor.

### **12.1.18. Tumor Samples**

All patients will have a mandatory core or excisional biopsy of lesion planned for MV-NIS injection (fine needle aspirate is not adequate) sent to a central lab for correlative research, performed retrospectively. This must be obtained within 21-day screening period before enrollment.

Post-treatment biopsy (12-15 days post-MV-NIS injection) will be after SPECT/CT imaging but before atezolizumab administration and include 6 core biopsies of the MV-NIS-injected lesion and 6 core biopsies of an uninjected lesion (if feasible). See the Lab Manual for further details and prioritization of processing in the case of insufficient material. Biopsies of injected lesion and an uninjected lesion may be repeated at day 36 (+/- 5 days) if feasible.

The Day 15 visit on the schedule of assessments ([Table 1](#)) may be split into 2 visits to permit flexibility in biopsy timing and recovery prior to atezolizumab treatment as follows: Day 12-15 the investigator may perform the biopsy, preceded by SPECT/CT, viral shedding, viremia, blood for flow cytometry, PBMCs for exosome and T cell tetramer assay; Day 15-16 perform the physical exam, history, vitals, PS and atezolizumab administration. Concomitant medications and AEs will be recorded at both time-points, as necessary.

### **12.1.19. Viral Shedding: Mouth Swab and Urine Specimens**

Mouth swabs should be collected as described in the Lab Manual.

Patients will collect a mid-stream urine sample of 100 cc. Specimens will be collected at screening and on day 15.

If a patient is found to be shedding the virus in urine or mouth swab specimens(s), family members who do not have documentation of immunity, will be offered testing to assess anti-measles virus immunity by Enzyme Immunoassay (Diamedix, see [section 3.18](#)) and testing of mouth swab specimens(s) for the presence of MV-NIS. Measles vaccination will be offered to seronegative individuals, as per standard clinical practice.

### **12.1.20. Assessment of Viremia**

Patient's peripheral blood will be monitored for evidence of measles virus viremia. This will be performed by quantitative RT-PCR.

Assessment of measles viremia will be performed at screening, day 3, 15 and 36 (if day 15 is positive). If at day 36, there is 10-fold increase in MV-NIS/mcg of RNA, repeat tests will be performed within 2 days to confirm the result. Weekly testing will be done thereafter until resolution to baseline.

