5. Biopsies to be obtained by radiologist under CT guidance. Pre-treatment biopsy will be of lesion planned for MV-NIS injection. Biopsy 12-15 days post-MV-NIS injection will be after SPECT/CT imaging but before atezolizumab administration and include 6 core biopsies of the MV-NIS-injected lesion and 6 core biopsies of an uninjected lesion (if feasible). See lab manual for further details and prioritization of processing in the case of insufficient material. Biopsies of injected lesion and an uninjected lesion may be repeated at day 36 (+/- 5 days) if feasible. Biopsies for a) paraffin sections, b) exome and RNA sequencing, c) infectious virus recovery, d) qRT-PCR for viral RNA. Exome sequencing only at baseline. See lab manual for details on processing and collection.
6. Mouth swab and urine collection for shedding studies by infectious virus recovery. See lab manual for details on processing and collection.
7. Assessment of viremia: Collect 2.5 ml blood into PAXgene tube (2 tubes). Perform at day 3, 15 and 36 (if day 15 is positive). If at day 36, there is 10-fold increase in MV-NIS/mcg of RNA, repeat tests will be performed within 2 days to confirm the result. Weekly testing will be done thereafter until resolution to baseline. See lab manual for details.
8. Research blood for a) immune phenotyping by flow cytometry, b) PBMC for exome and RNA sequencing, c) T cell analysis for neoantigen and tetramer assays. Exome sequencing done only at baseline. See lab manual for processing and collection.
9. Day 15 visit may be split into 2 visits to permit flexibility in biopsy timing and recovery prior to atezolizumab treatment as follows: Day 12-15 SPECT/CT, viral shedding, viremia, research blood for flow cytometry, PBMCs for sequencing and T cell assay must be performed PRIOR to tumor biopsy; Day 15-16 physical exam, history, vitals, PS and atezolizumab administration.
10. After Cycle 1, tumor measurements per RECIST 1.1 will be conducted every 3 cycles (i.e. cycles 4, 7, 10 etc.) until PD. For patients whose disease progresses, immune-related response criteria may be used by the investigator to continue therapy in the presence of potential pseudoprogression or tumor flare with clinical stability as appropriate until PD is confirmed.
11. Patients who discontinue atezolizumab for reasons other than disease progression will continue to have tumor evaluations every 12 weeks per standard of care until PD.

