#### 7.1.1.1. DLT definition

DLT will be defined as an AE that is not pre-existing due to malignancy, attributed (definitely, probably, or possibly) to the MV-NIS, occurring within 36 days of MV-NIS administration and meeting the following criteria:

Hematologic:	$\geq$ grade 3 as per NCI Common Terminology Criteria for Adverse Events (CTCAE) v4.03 except grade 3 ANC lasting < 72 hours.
Renal:	Serum creatinine $\geq$ 2 times baseline.
Viremia:	Lasting for $\geq$ 4 weeks after intratumoral injection.
Clinical measles:	Any grade per CDC definition ( http://www.cdc.gov/measles/hcp/index.html )
Other non-hematologic, including:	$\geq$ grade 3 AE as per NCI CTCAE v4.03.
• Allergic reactions	
• Autoimmune toxicity	
• Organ toxicity	

Note: in the case of grade 3-4 laboratory abnormalities, and any other clinically significant lab findings which potentially meet the definition of DLT, repeat tests must be performed every 1-2 days in order to verify duration accurately and observe recovery.

AEs meeting these definitions but related only to atezolizumab will not be considered a DLT.

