### **7.1.2. Conduct of escalation cohorts**

A standard 3+3 design will be used for the dose escalation part of the study. Starting at dose level 1 (refer to [Table 3](#)), three patients will be treated per dose level. The first three patients treated at dose level 1 will be enrolled at least 24 hours apart. All patients will be observed for a DLT period of 36 days after MV-NIS administration (which is 3 weeks after atezolizumab) and the last patient in each cohort must have completed the DLT period prior to each dose escalation decision. Resolution of viremia in all patients at a dose level is required prior to dose escalation being allowed.

If a DLT is observed, 3 additional patients will be enrolled at that dose level. If 1/6 patients experiences DLT, escalation may proceed; if  $\geq 2/6$  patients experience DLT, the MV-NIS dose will be de-escalated and 3 further patients added at the previous dose level. Dose level -1 will only be explored if dose level 1 is not tolerated. Doses will not be escalated in any individual patient. Any patient who experiences a DLT will be taken off study drugs, but will be followed up for response and PFS.

If no DLTs are seen at any of the dose levels, then the MTD will be the maximum delivered dose ( $1 \times 10^9$ ). MTD will be defined as the highest safely administered dose at which no more than one out of six or 0/3 patients experience DLT.

The first 6 patients of the expansion cohort will be enrolled and observed for 36 days after the 6th patient has received treatment prior to any additional patients being treated. If  $\leq 1/6$  DLT is observed then the remaining patients will be enrolled and treated sequentially, with no waiting period or limitation on simultaneous enrolment. If  $\geq 2/6$  patients in the expanded cohort experience a DLT, then the entire expansion cohort will be re-enrolled at the next lower dose level.

If a patient fails to complete the initial course of therapy (defined as study drug administration and four weeks of observation) for reasons other than adverse events or disease progression based on the day 36 CT-scan, then the patient will be regarded as non-evaluable for DLT and an additional patient will be treated at the current dose level. However, all AE information from patients who received any study treatment will be utilized in the analysis.

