#### **5.2 Immune-Related Hepatitis**

Immune-mediated hepatitis, defined as requiring use of corticosteroids and with no clear alternate etiology, occurred in patients receiving TECENTRIQ treatment. Liver test abnormalities occurred in patients who received TECENTRIQ. Monitor patients for signs and symptoms of hepatitis. Monitor AST, ALT, and bilirubin prior to and periodically during treatment with TECENTRIQ. Administer corticosteroids at a dose of 1–2 mg/kg/day prednisone equivalents for Grade 2 or greater transaminase elevations, with or without concomitant elevation in total bilirubin, followed by corticosteroid taper. Withhold TECENTRIQ for Grade 2 and permanently discontinue TECENTRIQ for Grade 3 or 4 immune-mediated hepatitis [*see Dosage and Administration (2.2) and Adverse Reactions (6.1)*].

Across clinical trials (n=1978), Grade 3 or 4 elevation occurred in ALT (2.5%), AST (2.3%), and total bilirubin (1.6%).

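### The viremia and laboratory sampling schedule can miss DLTs that the primary endpoint counts, so the DLT rate may be underestimated

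*Combined protocol and SAP*

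**What the plan says.** Section 7.1.1.1 counts DLTs within 36 days of MV-NIS. They include viremia that lasts for at least "4 weeks after intratumoral injection", hematologic toxicity of grade 3 or higher (except grade 3 ANC lasting under 72 hours), and creatinine at least twice baseline. Events related only to atezolizumab are not DLTs. Under Section 7.1.2 the MTD is the highest dose with 0/3 or at most 1/6 patients with a DLT.

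For viremia sampling, Section 12.1.20 states: "Assessment of measles viremia will be performed at screening, day 3, 15 and 36 (if day 15 is positive". Table 1 footnote 7 agrees. Footnote 9 lets the Day 15 samples be drawn from Day 12. On retesting, Section 12.1.20 says: "If at day 36, there is 10-fold increase in MV-NIS/mcg of RNA, repeat tests will be performed within 2 days". After that, tests are repeated each week until return to baseline. Section 7.1.2 adds a condition: "Resolution of viremia in all patients at a dose level is required prior to dose escalation being allowed".

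Table 1 schedules hematology and chemistry at baseline, Day 8, Day 36 and later cycles. Day 15, the first atezolizumab infusion, has none. Footnote 9 lists the second part of that visit as "Day 15-16 physical exam, history, vitals, PS and atezolizumab administration". The first part has imaging, virology and research blood, then the biopsy.

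**The concern.** The DLT count drives each escalation decision, the MTD, and the check on the first six expansion patients. A criterion defined by duration or by a laboratory value can be counted only if a sample falls where the criterion can be met. Here the 4-week viremia threshold falls between two sampling days, and laboratory criteria go 27 days without a scheduled test. Section 5.2 suggests that laboratory toxicity is a realistic prospect. In the IV study it lists grade 3-4 neutropenia (n=10), thrombocytopenia (n=5), anemia (n=2) and lymphopenia (n=1) as at least possibly related, and one grade 4 neutropenia was a DLT. Route and dose differ from this trial, so this shows plausibility and does not give a rate.

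An uncounted DLT can only lower the observed rate, and so makes escalation more likely.

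**Working it through.** **Inputs.** Injection is Day 1 (Section 12). Viremia days are 3, 15, and 36 if Day 15 is positive (Section 12.1.20). Laboratory days within the window are 8 and 36, each ±1 day (Table 1). The escalation rule is 0/3 or 1/6 (Section 7.1.2). The documents give no operating characteristic for DLT detection or for the 3+3 design, so there is no stated figure to reproduce. The error rates printed for the response rule (at least 8 of 21) do reproduce, at α = 0.04305 and power 0.8029, but they are not inputs here.

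**Step 1: viremia calendar.** Four weeks after Day 1 is Day 1 + 28 = Day 29.
- Positive on Days 15 and 36: Day 36 is 35 days after injection, so the viremia is observed and supports a DLT.
- Positive on Day 15, negative on Day 36: a last positive day of 15 to 28 is not a DLT, and one of 29 to 35 is. The two cannot be told apart. The blind band is 36 − 29 = 7 days, or 6 to 8 with the ±1 day window.
- Negative on Day 15: no later test, so viremia that appears or returns after atezolizumab starts is not looked for.

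Two assumed clearance models illustrate the size. If clearance is uniform between Days 15 and 36, (36 − 29)/(36 − 15) = 7/21, or one third, of patients positive on Day 15 and negative on Day 36 met the definition. If clearance is exponential with half-life h, the share of patients viremic on Day 29 who are still positive on Day 36 is 0.5^(7/h). For h = 3.5, 7, 14 and 28 days that is 25%, 50%, 71% and 84%, so 75%, 50%, 29% and 16% would read negative.

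**Step 2: retest trigger against the other rules.** The DLT criterion is duration. The escalation condition is resolution in all patients. The retest trigger is a 10-fold rise with no reference value. A patient still positive on Day 36 without that rise meets the first, fails the second and does not meet the third. Whether weekly testing covers this patient is unclear.

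**Step 3: laboratory detection.** Days 9 to 35 (35 − 9 + 1 = 27 days) have no scheduled panel. Assume a laboratory-only event of fixed duration with onset equally likely on each of Days 2 to 36 (35 days). It is detected if it covers a scheduled day. For a 7-day event, onset on Days 2–8 covers Day 8 and onset on Days 30–36 covers Day 36, so detection is 14/35 = 40%. A Day 15 panel adds onsets on Days 9–15, giving 21/35 = 60%.

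| Duration (days) | Days 8, 36 | Days 8, 15, 36 |
|---|---|---|
| 3 | 6/35 = 17% | 9/35 = 26% |
| 7 | 14/35 = 40% | 21/35 = 60% |
| 14 | 21/35 = 60% | 28/35 = 80% |
| 21 | 28/35 = 80% | 35/35 = 100% |

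**Step 4: effect on one escalation decision.** With true DLT rate p and overall detection s, set q = p × s. Then P(escalate) = (1 − q)³ + 3q(1 − q)⁵. If a share w of DLTs is laboratory- or viremia-only and a fraction d of those is detected, s = 1 − w(1 − d). At p = 0.33 and d = 0.40 (both assumed):
- full detection: 0.434
- w = 0.10, s = 0.94: 0.474
- w = 0.25, s = 0.85: 0.535
- w = 0.50, s = 0.70: 0.641

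**The case against.** A reader might infer that the schedule cannot observe these DLTs at all. It can observe many. Viremia positive on Days 15 and 36 is seen. A laboratory toxicity present on Day 8 or Day 36 is seen, and repeat tests every 1 to 2 days then follow. Symptomatic DLTs and clinical measles do not depend on these samples, since AEs are assessed throughout, Day 15 includes history and examination, and unscheduled visits may include laboratory tests. All of this stands. What it does not cover is an asymptomatic value that resolves between scheduled panels, because the repeat-test rule starts only after an abnormality has been found.

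A reader might also infer that the escalation condition cannot be enforced. A negative Day 36 test documents resolution, a negative Day 15 test does so as of that day, and a positive Day 36 test blocks escalation until resolution is shown. Weekly testing could be read to include every unresolved patient, and footnote 7 refers to a laboratory manual not among the documents. The ambiguity remains, but the condition is not void.

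Two tempting supports fail. The appended label says "Monitor AST, ALT, and bilirubin prior to and periodically during treatment with TECENTRIQ", but all three tests are in the chemistry panel drawn at baseline and Day 8, before the first infusion, and that sentence does not ask for a same-day sample. The Day 36 viremia cell in Table 1 is no evidence of sampling in all patients, because footnote 7 makes it conditional.

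The detection figures also depend on duration. Longer events are mostly caught, the shortest grade 3 neutropenia is excluded by definition, and uniform onset after a single injection is only an assumption.

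**Conclusion.** The point holds as a risk of undercounting, and it should be fixed. As written, the plan can leave uncounted viremia that clears on Days 29 to 35, viremia that appears or returns after a negative Day 15 test, and transient laboratory-only DLTs on Days 9 to 35. An abnormality first seen on Day 36 is also hard to attribute to MV-NIS or to atezolizumab only, because no panel separates the two exposures after Day 8.

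The direction follows from the documents: missed events lower the observed DLT rate. The size does not. It depends on the share of DLTs that are laboratory- or viremia-only, on their duration and onset, and on viral clearance, none of which is given. The percentages above are illustrations under stated assumptions. A reader might conclude that the MTD will be set too high. The documents do not support that. Nor do they say that a patient positive on Day 15 and negative on Day 36 would be scored as free of DLT, since they give no rule for this case.

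**What to change.** Reconcile four items so that each criterion can be determined from a scheduled sample: the viremia DLT definition (Section 7.1.1.1), the viremia sampling days and the Day 36 retest trigger (Section 12.1.20 and Table 1 footnote 7), and the resolution requirement (Section 7.1.2). State how a patient positive on Day 15 and negative on Day 36 is classified, give the reference value for the 10-fold increase, and say whether weekly testing covers a patient still positive without that rise. Which clinical threshold applies is for the sponsor and investigators to settle.

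Take the Day 36 viremia sample in all patients. Add hematology and chemistry to the existing Day 15 visit, before the infusion. This raises detection as shown in the table and gives a pre-atezolizumab value for attribution.

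The cost is protocol wording, one blood sample (in patients negative on Day 15) and one standard panel per patient at existing visits. A few more DLTs may be found. A Day 15 panel still leaves Days 16 to 35 without a scheduled test, so some short events would remain undetected.
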